**b. Describe the research methods, including how the study will be implemented locally.**

The research involves (1) neurocognitive testing, (2) practice on cognitive tasks, and (3) performing MRI scans. (1) Neurocognitive testing will be done at the Martinez VA Research Building 4, Outpatient Clinic, Brain Health Building and/or Center for Rehabilitation and Extended Care (CREC); (2) practice on cognitive tasks will be done at the Martinez VA Research Building 4, Outpatient Clinic, Brain Health Building and/or Center for Rehabilitation and Extended Care or at home; and (3) performing fMRI scans will be done at the Brain Imaging Center.

**c. Provide detailed information about all study procedures, including the approximate duration and frequency of each procedure. It is not necessary to repeat descriptions of non-human related procedures from the protocol narrative (e.g. you should describe how much and how frequently blood is drawn, but not the methods for performing tests on the blood, if already stated elsewhere).**

\_\_\_ Neurocognitive measurements: This part of the experiment takes approximately 2 - 3 hours. The subject is free to take breaks throughout the session. Subjects may undergo neurocognitive measurements once if they do not undergo cognitive training, twice if they participate in short-term or medium-term training (pre- and post-training), and three times if they participate in long-term training (at baseline, 5 weeks, and 10-weeks)

\_\_\_ Cognitive task practice: These may be of short, medium and long-term duration in 3 separate stages. In the first stage, subjects may be asked to practice tasks for a single session. The short-term practice tasks involve presentations of images or words on a computer during one session lasting up to 90 minutes. In the second stage, subjects may be asked to practice tasks over 2-4 weeks. This medium-term training also involves practicing tasks that involve attention and memory for 30-60 minutes a day. Subjects will be randomized into groups doing the same tasks, but in a different order. In the third stage, subjects may be asked to participate in cognitive task practice that is designed to be a form of cognitive rehabilitation training. This long-term training includes practicing 1-2 hours each day for up to 10 weeks working on cognitive tasks that engage attention, working memory, goal management and other executive functions, or education sessions about brain health, with a therapist on an individual basis and in groups.

\_\_\_ fMRI scanning: A session typically takes 60-90 minutes and the subject is given frequent breaks. The subject may stop the experiment at any time. Subjects may undergo fMRI once if they do not undergo cognitive training, twice if they participate in short-term or medium-term training (pre- and post-training), and three times if they participate in long-term training (at baseline, 5 weeks, and 10-weeks)

\_\_\_ EEG studies: A recording session typically takes 60-90 minutes. The subject is given breaks every 5-10 minutes, but may request a break or stop the experiment at any time. These will be done in Research Building 4 at VANCHCS Martinez.

\_\_\_ Follow-up contact: Researchers will contact subjects by telephone 6 months after other study activities to ask standardized questions about their post-participation level of functioning in various life domains. Telephone contact takes 30-60 minutes. Subjects may also be asked to return six months after their first visit for follow-up neurocognitive testing and MRI.

**d. Distinguish procedures that are for research from those that are clinically indicated and/or standard of care. All the procedures are for research.**

e. **Will any study procedures (including analysis of subject samples or data) be conducted at any site other than VANCHCS/VACCHCS?**

Yes  No

• If "YES", complete the following information:

1) **Site(s):** University of California, Berkeley and outpatient subjects' homes

2) **What study procedures will be performed there?** fMRI at UC Berkeley Brain Imaging Center. Outpatient subjects will have option to participate in computer-assisted cognitive training at home or in Research Building 4 at VANCHCS Martinez or the Martinez VA Center for Integrated Brain Health and Wellness.

## H. RISK

### 1. Expected risks

- Describe all known risks to subjects of study-related procedures and products and their expected frequency and severity.
- Assess the likelihood and seriousness of identified risks.

a. **Physical Risks:** The research procedures involved in this study present minimal physical risk to the subjects. MRI Studies: Subjects will be repeatedly queried about metal in their bodies and claustrophobia before undergoing MRI. The risks for 3T and 4T MRI are the same as for clinical MRI scans, typically at 1.5T. The risks of this procedure will be attenuated for those patients who have undergone acute MRI as verified by the acute images or notes in their charts. If CT rather than MRI was taken acutely, the reasons will be established before considering that patients participation in the MRI portion of this project. Although MRI scanning is painless, subjects may experience discomfort. In particular, subjects may be bothered by the beeping and hammering sounds made when the scanner is collecting measurements. Some people become claustrophobic inside the magnet. Subjects may also experience peripheral stimulation, manifested as a gentle tap or sensation of mild electric shock. Because the MRI scanner attracts certain metals, it could move metallic objects within the MRI room which could possibly harm a subject. Further, because of the high magnetic field, people with pacemakers, heart rhythm disturbances, permanent cosmetics or certain metallic implants will be excluded. Finally, because the risks to a fetus from MRI are unknown, all women will have a pregnancy test immediately prior to scanning. Disposable earplugs will be provided to diminish the noise. Subjects with a history of claustrophobia will be excluded. Precautions have been taken to prevent metallic objects from moving within the MRI room. If a subject is uncomfortable for any reason, the experiment will be stopped. They will be warned about claustrophobia and will be given earplugs or headphones in fMRI study to reduce the noise intensity. They will also be given a hand held buzzer that sounds in the exterior room when pressed to indicate that they are uncomfortable or want to discontinue the imaging procedure. When this occurs subjects will be immediately removed from the scanner.

EEG Studies: Conventional EEG recording with standard subject grounding procedures are always employed. Subjects may become bored or anxious during the course of EEG measurements. The anxiety infrequently encountered can be immediately addressed and the EEG recording will be aborted, if requested.

b. **Psychological Risks:** The research procedures involved in this study present minimal psychological risk to the subjects. The primary risk in this study is the potential for anxiety, discomfort or boredom associated with completing neuropsychological testing, fMRI or EEG testing, and treatment intervention. The behavioral test battery is relatively brief and is non-invasive. It consists of instruments (neuropsychological and functional assessments, and self-report questionnaires) that have been previously administered to different patient populations, thus the potential for creating undue anxiety or frustration is minimal. There is a possibility of fatigue or boredom from performance of cognitive tasks. Participants are allowed frequent breaks during training. For patients, training will be adjusted for the fatigue level, and training sessions will stop if patients are frustrated or fatigued.

c. **Social Risks:** There are no perceived social risk.

d. **Economic Risks:** There are no perceived economic risks.

e. **Legal Risks:** There is a real, but small risk of breach of confidentiality. This risk will be minimized by controlling data storage.

## 2. Risk minimization

a. **Describe the impact of study design on risk.** (e.g. does observational design impact on risk; or does observational design only impact privacy risks; or does placebo controlled design impact risk, or do all patients receive therapy; or does single blind placebo washout period increase risk of uncontrolled symptoms?)

The study is designed in a series of parts. First, participants are enrolled in a cross-sectional study involving neurocognitive and functional MRI testing. Risks associated with this portion are related to time consumption, potential boredom and risks to privacy. Additional portions of the study include an experimental cognitive task practice interventions, in which participants are randomized prospectively to different groups which do the same tasks, but in different orders. The risks of boredom and fatigue increase.

b. **Describe study procedures that minimize risks.**

Psychological:

\_\_The behavioral test battery is relatively brief and is non-invasive. It consists of instruments (neuropsychological and functional assessments, and self-report questionnaires) that have been previously administered to different patient populations, thus the potential for creating undue anxiety or frustration is minimal.

\_\_Cognitive training: There is a possibility of fatigue or boredom from performance of cognitive tasks. Participants are allowed frequent breaks during training. For patients, training will be adjusted for the fatigue level, and training sessions will stop if patients are frustrated or fatigued.

Physical:

\_\_MRI: The risks of this procedure will be attenuated for those patients who have undergone acute MRI as verified by the acute images or notes in their charts. If CT rather than MRI was taken acutely, the reasons will be established before considering that patients participation in the MRI portion of this project. Although MRI scanning is painless, subjects may experience discomfort. In particular, subjects may be bothered by the beeping and hammering sounds made when the scanner is collecting measurements. Some people become claustrophobic inside the magnet. Subjects may also experience peripheral stimulation, manifested as a gentle tap or sensation of mild electric shock. Because the MRI scanner attracts certain metals, it could move metallic objects within the MRI room which could possibly harm a subject. Further, because of the high magnetic field, people with pacemakers, heart rhythm disturbances, permanent cosmetics or certain metallic implants will be excluded. Finally, because the risks to a fetus from MRI are unknown, all women will have a pregnancy test immediately prior to scanning. Disposable earplugs will be provided to diminish the noise. Subjects with a history of claustrophobia will be excluded. Precautions have been taken to prevent metallic objects from moving within the MRI room. If a subject is uncomfortable for any reason, the experiment will be stopped. They will be warned about claustrophobia and will be given earplugs or headphones in fMRI study to reduce the noise intensity. They will also be given a hand held buzzer that sounds in the exterior room when pressed to indicate that they are uncomfortable or want to discontinue the imaging procedure. When this occurs subjects will be immediately removed from the scanner.

\_\_Conventional EEG recording with standard subject grounding procedures are always employed. Subjects may become bored or anxious during the course of EEG measurements. The anxiety infrequently encountered can be immediately addressed and the EEG recording will be aborted, if requested.

\_\_Privacy: We recognize the need to guaranteed participants confidentiality in order to protect individual participants from potential embarrassment, as well as to obtain maximally valid data. All information will be kept confidential in accordance with all regulations as specified by the Department of Veterans Affairs. All patient data will be depersonalized after initial screening and enrollment into the study. All personally identifying information will be kept in locked cabinets or password protected files.

**c. Describe standard of care procedures that minimize risks.**

There is no clear national standard of care for rehabilitation treatments for patients with brain injuries. However, most of our subjects receive high quality medical care at the VANCHCS by qualified professionals including physicians, psychologists and therapists. Neurologic and neuropsychologic evaluation, CT and/or MRI scans are all part of standard of care in our practice.

**I. RISK BENEFIT RATIO**

**1. Risks in Relation to Benefits**

**a. What are the direct benefits to the participants?**

There are no definite direct benefits to the subjects. The findings from these studies may potentially make a major impact in improving rehabilitation for patients with brain injuries, leading to a direct benefit to society.

**b. Why do you believe the risks are reasonable in relation to the potential benefits to the participants?**

The risks of this research to subjects are minimal. There are no definite direct benefits to the subjects.

**c. What are the benefits to society?**

As noted in the introduction, improved treatments for executive control dysfunction would potentially make a major impact in improving outcomes after brain injuries. The findings from these studies will be presented to health care workers and to other scientists in the field, and this is expected to influence both clinical care and future scientific investigations.

**Why do you believe the risks are reasonable in relation to the potential benefits to society?** The risks of this research to subjects are minimal, and therefore the risk is reasonable in relation to the potential benefits to society.

**2. Alternatives to participation**

**a. Describe appropriate alternative procedures or courses of treatment, if any, which might be advantageous to the participant. (If no alternatives exist or if this is not a treatment study, state so.)**

This is not a treatment study. Subjects may decline participation in these studies, or discontinue participation at any time. Declining to participate in the studies will not have any effect on standard clinical care.

**J. MONITORING SAFETY**

**1. Describe the Data and Safety Monitoring Plan that ensures the safety of participants in this research study. (e.g. what labs to monitor for abnormalities, what questionnaire responses to monitor for suicide)**

All patients will be seen by the PI or his research staff. Research subjects will continue to receive usual care. Although this is a minimal risk study, the PI and investigators will monitor study subjects for adverse events during the study. Monitoring will occur continuously during study activities. Although the only interventions are behavioral, a standard grading scale will be used to describe AEs if the need arises: 0=none, 1=mild, 2=moderate, 3=severe, 4=life-threatening, 5=fatal. The attribution scale is 1=definitely not related, 2=probably not related, 3=possibly related, 4=probably related, 5=definitely related to the study interventions. The PI will promptly report any serious adverse events or unanticipated problems involving risks to study subjects in accordance with regulations: reportable adverse effects arising from any of the research procedures will be submitted promptly to the IRB. Although they are not anticipated to occur, unanticipated problems (involving risks to subjects) or Serious Adverse Events in subjects will be reported to the IRB within 5 working days of awareness of the event. Copies of reports will be submitted to the IRB so that they are received no later than 15 calendar days after the event. In addition, adverse events in all categories will be included in the PIs reports to the IRB as required by the federal regulations. All reportable adverse events will be compiled, and reported in summary form, on an annual basis to the IRB, and at the conclusion of the study. The PI reviews and reports on the progress of the study on an annual basis. The PI will monitor study progress, outcomes and participant safety, and may make recommendations on changes to the study protocol. The PI will review safety on an ongoing basis. [name] will perform the safety monitoring.

**2. Does this study have a Data and Safety Monitoring Board (DSMB)?**  
 Yes  No  
 • If "YES":  
 a. What is the nature and expected role of the DSMB?  
 b. How often will the findings of the DSMB be reported to the IRB?

**3. Explain how researchers will manage adverse events and research-related injuries.**  
 All research staff have been directed to document adverse events and to notify the Principal Investigator of any adverse event. Investigators will follow up with subjects until the resolution of the adverse event and will ensure that appropriate medical care is provided.

**4. Describe the circumstances under which a participant may be withdrawn prematurely from the study and the potential risks of such early withdrawal.**  
 A participant may decide to withdraw or be withdrawn for a variety of medical and personal reasons, such as lack of interest, non-participation, or change in medical condition. A potential risk of early withdrawal would be the possible adverse effect on the participant's self-esteem (e.g., feeling like a failure). This risk would be addressed by supportive counseling of participants who are withdrawn prematurely.

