**Experimental Intervention (the investigator observes the effect of the intervention on outcome):**

Randomized

Blinded

Retrospective

Prospective

**5. Describe statistical methods** (For example: sample size estimation, power calculation, statistical tests or descriptive statistics, data analysis tools, etc.)

Analyses of cross-sectional data will include (a) across-group comparisons using univariate statistics and (b) within group correlational analyses testing the relationships between behavioral and neural measurements. Tests of repeated measures will be used to assess the effects of the training interventions on pre- and post- intervention measurements. Intervention group x time interactions will be assessed using ANOVA and specific relationships will be tested using paired T-tests.

**6. Describe appropriateness and rationale for elements warranting special attention** (placebo, washout period, challenge study, radiation exposure, deception study, deviation from accepted standard of care).

n/a

**7. Have there been IRB approved protocol amendments modifying the study** (including sponsor amendments) since the last review?

Yes  No

- If "YES", list approval date and summarize the nature and purpose of all protocol amendments made since the time of last Initial or Continuing Review:

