\_\_Cognitive task practice: Subjects (patients and healthy volunteers) participate in cognitive task practice requiring attention and memory. These may be of short, medium and long-term duration in 3 separate stages. In the first stage, subjects may be asked to practice tasks for a single session. The short-term practice tasks involve presentations of images or words on a computer during one session lasting up to 90 minutes. In the second stage, subjects may be asked to practice tasks over 2-4 weeks. This medium-term training also involves practicing computerized cognitive tasks that involve attention and memory for 30-60 minutes a day. Subjects will be randomized into groups doing the same tasks, but in a different order. In the third stage, subjects will be asked to participate in cognitive task practice that is designed to be a form of cognitive rehabilitation training. This long-term training includes computer-assisted and therapist-guided practice 1-2 hours each day for up to 6 weeks working on cognitive tasks that engage attention, working memory, goal management and other executive functions, and may also include up to 6 weeks attending education sessions about brain health, with a therapist on an individual basis and in groups. The long-term training will include sessions with staff at the Martinez VA Outpatient Clinic, Brain Health Building and/or Center for Rehabilitation and Extended Care (CREC) on a weekly basis. Subjects in this third stage are also randomized into groups that do the same tasks, but in a different order. Assignments and materials for practicing at home will be given to patients and healthy volunteers. For computerized tasks, software for practicing tasks at home will be offered to participants. Subjects may stop participating at any time. Typically, neurocognitive testing and fMRI studies are performed before and after training.

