\_\_Functional MRI measurements: In the MRI test, subjects (patients and healthy volunteers) are asked to lie on their backs in the MRI scanner and perform a cognitive task. When the subjects are ready to be scanned, an MRI imaging coil will be placed around the subject's head. The subject will not come into contact with the coil during the experiment. Foam pads will be placed around the subject's head to limit head movement during the study. Functional MRI will involve scanning during the performance of a cognitive task and during rest. The cognitive task will involve presentation of images or words on a computer monitor or sounds through headphones. The subjects are asked to respond to certain stimuli by pressing a button. Basic structural images will be taken for reference to align with the functional images (these are separate from the clinical structural MRI imaging done as standard of care). Scanning will be performed using a 3 Tesla Siemens or 4 Tesla Varian scanners under the supervision of the Director of the Brain Imaging Center, [name] [name] or co-investigator [name].. All MRI studies performed at the Brain Imaging Center are part of research protocols and are not intended to provide comprehensive clinical MRI examinations of the brain. If a potential abnormality is identified on an MRI scan, the PI will immediately notify the subject and the family physician.

\_\_EEG studies: In EEG studies, EEG is recorded while concurrently monitoring behavior. Subjects (patients and healthy volunteers) are asked to sit in a soundproofed room and have EEG electrodes placed on their scalp with conducting paste. The experiments involve presentation of images on a computer monitor, sounds

through headphones, or taps to fingers. The subject is asked to respond to certain stimuli by pressing a button. All stimuli are presented at a comfortable level. A recording session typically takes 60-90 minutes. The subject is given breaks every 5-10 minutes, but may request a break or stop the experiment at any time. These will be done in Research Building 4 at VANCHCS Martinez. \_\_\_ Follow-up contact: Researchers will contact subjects by telephone 6 months after other study activities to ask standardized questions about their post-participation level of functioning in various life domains. Telephone contact takes 30-60 minutes. Subjects may also be asked to return six months after their first visit for follow-up neurocognitive testing and MRI.

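### People withdrawn for undefined non-participation have no stated continued assessment, and the pre/post tests in standard form leave them out, so the randomised comparison can be selected on behaviour after randomisation

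*Combined protocol and SAP*

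**What the plan says.** Section J.4 (premature withdrawal) answers a question about leaving the study, not only the training: "A participant may decide to withdraw or be withdrawn for a variety of medical and personal reasons, such as lack of interest, non-participation". It sets no threshold for non-participation. The only thing it describes afterwards is supportive counselling; J.3 adds follow-up of adverse events until they resolve.

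Section G.2.c schedules neurocognitive testing and fMRI at baseline, 5 weeks and 10 weeks for long-term training. The later follow-up is: "Researchers will contact subjects by telephone 6 months after other study activities to ask standardized questions", and "Subjects may also be asked to return six months after their first visit for follow-up neurocognitive testing and MRI". Neither sentence says whether people who were withdrawn are included.

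Section D.5 is the only statistical section supplied. It says: "Tests of repeated measures will be used to assess the effects of the training interventions on pre- and post- intervention measurements", and "Intervention group x time interactions will be assessed using ANOVA and specific relationships will be tested using paired T-tests". It gives no analysis set, no statement on analysis by assigned group, and no handling of missing scores.

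On the randomised comparison, G.2.a says: "Subjects in this third stage are also randomized into groups that do the same tasks, but in a different order". Section M.1 gives interim results, with p-values, for 22 Veterans who completed after randomisation to GOALS or brain health education. It does not give the number randomised or lost in each arm. Section F.3 reports 0 withdrawals since the last IRB report, a period in which 6 people entered. Section E.3 closes enrolment.

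**The concern.** Randomisation makes the groups comparable at entry. It protects the result only if the people analysed are the people randomised. Here, someone who does not take part can be withdrawn from the study, no text provides for the post-training score to be collected, and the planned tests then pass over that person. If this happens more in one arm, or for different reasons in the two arms, the group-by-time contrast mixes the training effect with a difference in who remained. A reader could not detect this, because no per-arm flow is given. Missing scores also cost precision in a data set whose only reported completed comparison has 22 people.

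**Working it through.** **No figure to reproduce.** D.5 states no alpha, power, SD, effect size or dropout rate. The accrual figure of 210 has no derivation. Every loss rate and correlation below is therefore an assumption.

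**Bias when loss is linked to the part of the outcome that baseline does not explain.** Suppose the least adherent share q of an arm has no post score, adherence is normally distributed, and adherence correlates r with the post score through the part not explained by baseline. The mean of those who remain shifts by r × m(q) SD of the score, with m(q) = φ(z_q)/(1−q):

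- m(0.1) = 0.1755/0.9 = 0.195
- m(0.2) = 0.2800/0.8 = 0.350
- m(0.3) = 0.3477/0.7 = 0.497

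Bias in the contrast = r × [m(q₁) − m(q₀)] when r is the same in both arms:

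| Loss, arm 1 vs arm 0 | r = 0.3 | r = 0.5 |
|---|---|---|
| equal | 0 | 0 |
| 20% vs 10% | 0.046 | 0.077 |
| 30% vs 10% | 0.091 | 0.151 |
| 20% vs 0% | 0.105 | 0.175 |
| 30% vs 0% | 0.149 | 0.248 |

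The sign reverses if the other arm loses more. Equal loss is not enough by itself: at 20% in both arms, with r = 0.3 or 0.5 in one arm and 0 in the other, the bias is 0.105 or 0.175 SD.

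**Bias when loss is linked only to baseline.** With adherence–baseline correlation a and baseline-to-post correlation 0.6, the change-score bias is −(1 − 0.6) × a × [m(q₁) − m(q₀)]. For a = 0.3 and 0.5 this is −0.019 and −0.031 SD (20% vs 10%), and −0.036 and −0.060 SD (30% vs 10%).

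**Which part a model can remove.** In a simulation with 1,000,000 per arm and no true effect, conditioning on baseline took the baseline-linked bias to 0.00. The residual-linked bias, 0.045 to 0.15 SD in the 20% vs 10% and 30% vs 10% cases, was the same before and after conditioning.

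**Scale against sampling error.** Assume the 22 completers split 11 and 11, with correlation 0.6.

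- SE of the difference in change = √(2(1 − 0.6)) × √(2/11) = 0.381 SD.
- SE adjusted for baseline = √(1 − 0.36) × √(2/11) = 0.341 SD, about 10% smaller.
- False-positive rate of a nominal 5% test (noncentral t, 20 df, ignoring the small change in variance from selection): 5.2% for a bias of 0.046, 6.7% for 0.151 and about 9.5% for 0.248.
- At correlation 0.8 the SE is 0.270 SD, and the last two become 8.3% and about 14%. With r = 0.5 that case needs an adherence–residual correlation of 0.5/0.6 = 0.83, which is extreme.

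**What the withdrawal count can say.** For 0 of 6, the exact two-sided 95% upper limit is 1 − 0.025^(1/6) = 46%.

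**The case against.** The strongest reply is that J.4 sits in the safety part of an IRB continuing-review form, and its question does not ask about outcome collection. Consent pages were removed, and the form refers to a protocol narrative that is not supplied separately. Silence is therefore weak evidence that no rule exists. This stands as a limit: the point concerns the supplied text only.

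Second, non-participation may mean not attending at all. The score is then missing whatever J.4 says, and continued assessment would not help. H.1 and H.2 also adjust training to fatigue without withdrawing anyone. Both remarks are fair, and the undefined term leaves the matter open. The gap in D.5 remains under either meaning.

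Third, Aim 1 in D.3.c describes a comparator matched for time and attention, which may make losses similar. It may, but no per-arm figures allow a check.

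Some stronger readings are tempting, and the documents do not support them:

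- *Poor adherers were dropped from the 22.* M.1 says that these people completed. It does not say that anyone was excluded.
- *54 entered minus 22 completed gives the losses.* The 54 in F.2 are not split by stage or arm, and the study also recruits healthy volunteers and has a cross-sectional part.
- *Assessment is conditional on adherence.* In context, the G.2.c wording about taking part in long-term training separates the stages, which have one, two or three assessments.
- *Zero withdrawals shows there is no problem.* That count covers only the last reporting period.

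**Conclusion.** The point holds as a weakness of the plan as written, not as a demonstrated bias. Withdrawal for an undefined reason, no stated assessment afterwards, and tests that in standard form need both scores together allow a comparison selected after randomisation.

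Neither direction nor size can be taken from the documents. Under the assumptions shown, the bias runs from 0 to about 0.25 SD, with either sign. At 11 per arm and correlation 0.6, the upper case is about 0.65 SE. A reader might infer that the effect must be small, or that it must favour active training; neither follows, because the documents give no cumulative or per-arm loss and no correlation. The range is a set of scenarios, not a bound. The point merits a change, with medium confidence.

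**What to change.** 1. **D.5.** Beside the planned ANOVA, not in place of it, report a between-group analysis of everyone randomised, as assigned. Use a likelihood-based mixed model with baseline in the outcome vector and baseline means constrained equal. Take the contrast at the first assessment before the groups exchange tasks. Label the analysis as added after the M.1 results were known. State that it improves precision (SE 0.381 to 0.341 SD at an assumed correlation of 0.6) and removes selection through observed scores, but does not correct losses linked to unobserved response. The estimate may move either way.
2. **Participant flow.** Report numbers randomised, withdrawn with reasons, and analysed per arm, including for the 22 completers. This is the step most likely to show whether selection occurred.
3. **J.4.** For anyone still in the study, define non-participation and state that stopping training does not by itself end the already planned assessments for those who still consent. The right to leave at any time is unchanged. With enrolment closing, this will help few people.

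The cost is a few sentences, one added analysis of data already collected, and a flow table.

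A separate point bears on the timing in step 1. G.2.a gives "computer-assisted and therapist-guided practice 1-2 hours each day for up to 6 weeks" and "may also include up to 6 weeks attending education sessions about brain health", while G.2.c gives assessments at 5 and 10 weeks and training of up to 10 weeks. These texts must be reconciled before the time of the contrast is fixed.
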